### 9.1.3 Supplemental Analyses

Additionally, primary analysis based on ITT population will be repeated as a supplemental analysis.

## 9.2 Secondary Efficacy Endpoints

### Key secondary endpoints

- 
- Proportion of subjects achieving corneal healing at Week 8 assessed by the CRC
  - Proportion of subjects achieving corneal healing at Week 4 assessed by the CRC
  - Time to corneal healing based on assessments by the CRC
  - Time to  $\geq 20\%$  decrease in lesion size (maximum diameter) from baseline assessed by the CRC
  - Proportion of subjects achieving corneal healing at each of Week 4, and Week 8 sustained for two weeks until Week 10 assessed by the investigator
  - Proportion of subjects without persistent corneal staining during the study as assessed by the CRC
  - Proportion of subjects with complete corneal healing and without persistent corneal staining during the study as assessed by the CRC

The two time-to-event key secondary endpoints will be analyzed by a log-rank test at a two-sided alpha 0.05. Time associated with each treatment arm will be summarized using the Kaplan-Meier method and displayed graphically where appropriate. Confidence intervals (CIs) for the 25th, 50th and 75th percentiles will be reported by each treatment arm.

The two dichotomous key secondary endpoints will be analyzed using a Chi-squared test as in the analyses of the primary endpoint. The proportion and associated 95% confidence interval will be reported by each treatment arm.

Tipping point analyses will also be performed for the proportion of subjects achieving corneal healing at Week 8 assessed by the CRC.

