#### **13.3.1. Analysis of Primary Endpoint**

The primary efficacy endpoint is the proportion of subjects achieving complete corneal healing defined as absence of corneal staining in the area of the defect/ulcer (i.e., 0 mm lesion) at Week 8 and the absence of the corneal staining in the area of the defect/ulcer (i.e., 0 mm lesion) two weeks later at Week 10 as assessed by a central reading center. The primary efficacy endpoint

will be analyzed using a Chi-squared test at a two-sided alpha 0.05. The proportion and associated 95% confidence interval will be reported by each treatment arm.

Missing data of the primary efficacy endpoint will be imputed as follow:

- Subjects with missing Week 8 data for any reason will be imputed as non-responders
- Subjects who demonstrate corneal healing at Week 8 and are missing Week 10 data will be imputed as non-responders

Sensitivity analyses based on different missing data imputation rules will be conducted for the primary endpoint. Specific imputation rules are:

1. Completers Analysis (Week 8 Observed) Data Imputation

- Subjects who do not complete the Week 8 Visit will be imputed as missing
- Subjects who demonstrate corneal healing at Week 8 and are missing Week 10 data will be imputed as missing at Week 8

2. LOCF Data Imputation

- Subjects with missing Week 8 and/or Week 10 data will have their last observed data carried forward

In addition, instead of Chi-squared test, Cochran–Mantel–Haenszel (CMH) test stratified by stage 2 NK vs stage 3 NK will be used to analyze the primary endpoint as another sensitivity analysis.

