### 13.3.2. Analysis of Secondary Endpoints

#### Key secondary endpoints

- Proportion of subjects achieving corneal healing at Week 8 assessed by the CRC
- Proportion of subjects achieving corneal healing at Week 4 assessed by the CRC
- Time to corneal healing based on assessments by the CRC
- Time to  $\geq 20\%$  decrease in lesion size (maximum diameter) from baseline assessed by the CRC
- Proportion of subjects achieving corneal healing at each of Week 4, and Week 8 sustained for two weeks until Week 10 assessed by the investigator
- Proportion of subjects without persistent corneal staining during the study as assessed by the CRC
- Proportion of subjects with complete corneal healing and without persistent corneal staining during the study as assessed by the CRC

The two time-to-event key secondary endpoints will be analyzed by a log-rank test at a two-sided alpha 0.05. Time associated with each treatment arm will be summarized using the Kaplan-Meier method and displayed graphically where appropriate. Confidence intervals (CIs) for the 25th, 50th and 75th percentiles will be reported by each treatment arm.

The five dichotomous key secondary endpoints will be analyzed using a Chi-squared test at a two-sided alpha 0.05. The proportion and associated 95% confidence interval will be reported by each treatment arm.

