## **1.0 INTRODUCTION TO THE STATISTICAL ANALYSIS PLAN**

The statistical analysis plan (SAP) is based on protocol CSB-C20-003 ‘A Multi-center, Randomized, Double-masked, Vehicle-controlled, Parallel-group, Study to Evaluate the Safety and Efficacy of CSB-001 Ophthalmic Solution 0.1% in Stage 2 and 3 Neurotrophic Keratitis Subjects’, Version 5.0, dated 21 July 2023. It details the methodology to be used in analyzing the data and outlines the specifications in the Tables, Figures and Listings (TFLs) for data to be included for executing the final statistical analyses for this study.

The analyses specified in this document supersede any high-level analysis plan described in the protocol.

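### Seven key secondary endpoints have no testing order, no gate on the primary and no alpha adjustment, and SAP 9.2 counts two dichotomous key secondaries where it lists five

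*SAP*

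**What the plan says.** Protocol 13.3.2 and SAP 9.2 list the same seven key secondary endpoints. Two are times to event: CRC-assessed healing, and a 20% or greater fall in lesion size. Five are dichotomous: CRC healing at Week 8, CRC healing at Week 4, an investigator-assessed healing endpoint, and two that involve persistent staining.

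- **Time to event.** Both documents use a log-rank test. The SAP's words are "The two time-to-event key secondary endpoints will be analyzed by a log-rank test at a two-sided alpha 0.05".
- **Dichotomous, protocol.** "The five dichotomous key secondary endpoints will be analyzed using a Chi-squared test at a two-sided alpha 0.05".
- **Dichotomous, SAP.** "The two dichotomous key secondary endpoints will be analyzed using a Chi-squared test as in the analyses of the primary endpoint". It does not say which two, and it states no alpha here or for the primary in 9.1.1. The alpha has to come from Protocol 13.3.1, where the rule for the primary is: "will be analyzed using a Chi-squared test at a two-sided alpha 0.05. The proportion and associated 95% confidence interval will be reported by each treatment".
- **Two time points in one item.** "Proportion of subjects achieving corneal healing at each of Week 4, and Week 8 sustained for two weeks until Week 10 assessed by the investigator". Neither document says whether this is one test or two.
- **Precedence.** SAP 1.0: "The analyses specified in this document supersede any high-level analysis plan described in the protocol".

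Protocol Section 13 and SAP Sections 7 and 9 are where a multiplicity rule would be expected. They contain no testing order, no condition that the primary succeed first, and no division of alpha.

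**The concern.** Two things are wrong. First, the plan gives formal significance tests to a group of endpoints labelled key, but no rule joins them to the primary or to each other. Followed exactly, it allows a key secondary to be called significant at 0.05 after the primary has failed, and any one of the seven to be picked out.

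Second, the governing document miscounts the family. Read literally, SAP 9.2 gives a test to four of its seven key secondaries and leaves three without one, and the reader cannot tell which three. Whether the two-time-point item is one test or two is also open. These choices could end up being made after unblinding.

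The tests do not look merely descriptive. For exploratory endpoints the plan says that it will only describe (SAP 9.3). For CRC healing at Week 8, SAP 9.2 adds a tipping-point analysis, which SAP 9.1.2 defines as switching outcomes until significance is lost. That presupposes a significance claim on a key secondary. The tiers are also blurred: CRC healing at Week 8 appears again among the exploratory endpoints (Protocol 11.1.3, SAP 2.2.3), and the other secondary endpoints are analysed by the same methods as the key ones.

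**Working it through.** The documents state no familywise error rate, so there is no figure of the plan's own to reproduce.

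**Inputs**
- Alpha per test: two-sided 0.05 (Protocol 13.3.2 for all seven; SAP 9.2 for the two log-rank tests; for the SAP's chi-squared tests, by reference to the primary and so to Protocol 13.3.1).
- Number of tests k: 7 under Protocol 13.3.2 (2 log-rank + 5 chi-squared); 4 under SAP 9.2 read literally (2 + 2); 8 if the two-time-point investigator item is split (7 + 1).
- Interim looks: none (Protocol 13.5, SAP 7.6), so no further alpha is spent.
- Correlation between test statistics: not given. Values from 0.3 to 0.9 are assumed.

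**Formulas, with no true effect on any key secondary**
- Independent tests: P(at least one p<0.05) = 1 − 0.95^k.
  - k = 4: 1 − 0.95^4 = 0.185
  - k = 7: 1 − 0.95^7 = 0.302
  - k = 8: 1 − 0.95^8 = 0.337
- Upper bound under any dependence: k × 0.05, which is 0.20, 0.35 and 0.40.
- Positive correlation: normal test statistics with a common correlation ρ, simulated with 300,000 draws and two-sided rejection.

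| Tests | Basis | Independent | ρ = 0.5 | ρ = 0.9 | Bound |
|---|---|---|---|---|---|
| 4 | SAP 9.2, literal | 18.5% | 15.6% | 9.4% | 20% |
| 7 | Protocol 13.3.2 | 30.2% | 22.9% | 11.4% | 35% |
| 8 | Seven, investigator item split | 33.7% | 25.1% | 11.9% | 40% |

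For seven tests, ρ = 0.3 gives 27.2% and ρ = 0.7 gives 17.8%.

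Positive correlation is the realistic case. CRC healing at Week 8 is one of the two components of the primary. Time to CRC healing is built from the same reading-centre series as CRC healing at Weeks 4 and 8. The last key secondary, "Proportion of subjects with complete corneal healing and without persistent corneal staining during the study as assessed by the CRC", can be met only by primary responders, and they must also satisfy the preceding one, "Proportion of subjects without persistent corneal staining during the study as assessed by the CRC".

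These rates count false positives in either direction. Counting only those that favour CSB-001, seven independent tests give 1 − 0.975^7 = 16.2%, against a nominal 2.5%.

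**Effect of a gated fixed sequence.** Order the primary and the key secondaries, test each at 0.05, and stop at the first non-significant result. A false claim can then occur only if the first true null hypothesis in the order is rejected, which has probability at most 0.05. Familywise error over the primary and key secondaries is therefore at most 5% whatever the correlation.

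**The case against.** The strongest reply on the count is that the SAP displaces the protocol only for the analyses that the SAP specifies. Where it is silent, Protocol 13.3.2 can still apply, and that gives all five dichotomous endpoints a chi-squared test. The same seven items appear in every list, so the SAP's two may simply be out of date. Much of this stands. A reader might infer that three endpoints certainly go untested, or that the family cannot be counted at all. The documents do not support either inference: the list is stable, and only the split of the investigator item is open. What remains is a direct conflict between the SAP's count and both its own list and the protocol, in the document that claims precedence.

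A second reply is that no section of the supplied text says a claim will rest on a key secondary, so the confirmatory consequence is inferred. That is fair. Against it stand the key label, the stated alpha and the tipping-point analysis.

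On a fixed sequence, the reply is that list order is not stated to be priority order, and that failure at CRC Week 4 would block both time-to-event endpoints. This also stands. The order is the sponsor's choice, and what matters is that it is complete and fixed in advance. The supplied text does not define persistent staining. It begins partway through Protocol Section 6, so a definition may exist elsewhere, but one is needed before the two endpoints that use it enter a sequence.

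**Conclusion.** The concern holds: there is no multiplicity rule for seven key secondary endpoints, and SAP 9.2 has a wrong count. The size is about 30% for the protocol's seven tests if independent and 18.5% for the four that the SAP assigns. With positive correlation it is lower, at about 23% (ρ = 0.5) to 11% (ρ = 0.9) for seven. These rates assume no true effect on any key secondary and tests that hold their nominal 0.05; the correlations are assumptions.

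Three stronger readings are tempting and should be resisted.
- Thirty percent is not a ceiling. It is the independence value for seven tests, and the bound is 35%. Nor does it follow from the SAP's count, because running fewer tests lowers the rate.
- It is not accurate that both documents set 0.05 for every key secondary. The protocol does; the SAP states it only for the log-rank tests.
- The primary result is not compromised. It is one test at two-sided 0.05 with no interim look, and its type I error is unaffected.

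The count is wrong as written. The testing order is a cheap improvement, needed only if key secondary results are to support error-controlled claims.

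**What to change.** In SAP 9.2, change the number of dichotomous key secondaries from two to five and state two-sided 0.05 for their chi-squared tests.

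Pre-specify a complete fixed sequence. It starts only if the primary is significant at two-sided 0.05, tests each step at two-sided 0.05, and stops at the first non-significant result. The listed order is a workable default:

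1. CRC healing at Week 8
2. CRC healing at Week 4
3. Time to CRC healing
4. Time to a 20% or greater decrease in lesion size
5. Investigator-assessed healing at Week 4
6. Investigator-assessed healing at Week 8, sustained to Week 10
7. No persistent staining
8. Complete healing without persistent staining

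The sponsor may prefer another order, provided that it is fixed before unblinding. Report endpoints after the first failure, and all other secondary endpoints, with nominal p-values labelled as such. Remove CRC healing at Week 8 from the exploratory list so that it sits in one tier.

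The deadline is the controlled-phase data-point lock and unblinding in SAP 7.1, which comes before the uncontrolled phase ends.

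The cost is SAP wording only, with no new data and no change in sample size. The downside is that an endpoint after the first failure cannot support an error-controlled claim, however small its p-value.

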### **Other secondary endpoints**

- Time to corneal healing based on assessments by the investigator
- Proportion of subjects achieving a  $\geq 15$ -letter gain in the study eye from baseline in pinhole distance VA at each of Weeks 4 and 8

Time to event endpoint and dichotomous endpoint will be analyzed using the same statistical method as in the analyses of the key secondary endpoints.

### **9.3 Exploratory Efficacy Endpoints**

Descriptive summary statistics (e.g., frequency, mean, standard deviation, median, minimum, and maximum for continuous variables; frequency [%] for categorical variables) will be provided for the exploratory endpoints (see [Section 2.2.3](#) for listing of exploratory endpoints).

## **10.0 SAFETY EVALUATION**

### **10.1 Adverse Events**

---

AEs verbatim descriptions will be coded using a current version of MedDRA. A treatment-emergent adverse event (TEAE) will be defined as any AE that occurs on or after the start time of the first study drug administration.

An overall summary of TEAEs will be presented as the number and percentage of subjects with at least one event on the following categories:

- TEAEs
- Severe TEAEs
- Treatment-related TEAEs
- Severe and treatment-related TEAEs
- Serious TEAEs
- Serious treatment-related TEAE
- TEAEs leading to treatment discontinuation
- Treatment-related TEAEs leading to treatment discontinuation
- TEAEs leading to Death (with an outcome of Fatal)

TEAEs will be summarized by System Organ Class (SOC) and Preferred Terms (PT) by treatment group. A patient will be counted only once by the highest severity grade within a system organ class and preferred term, even if the patient experienced more than 1 TEAE within a specific system organ class and preferred term. Following incidence tables of TEAEs will be presented:

- TEAEs
- TEAEs by severity
- Treatment-related TEAEs
- Treatment-related TEAEs by severity
- Serious TEAEs

Systemic TEAEs and ocular TEAEs will be summarized separately. Ocular TEAEs will be summarized by study eye and non-study eye.

All AEs will be listed by subjects.

SAEs for death will be listed if applicable and a narrative included.

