#### **13.4. Safety Analysis**

The safety analysis set will be the primary population for safety evaluation. Summaries of AEs and other safety parameters will be provided by treatment arm, as appropriate.

AEs verbatim descriptions will be coded using a current version of the Medical Dictionary for Regulatory Activities (MedDRA).

An overall summary of subjects with AEs and SAEs will be tabulated with numbers and percentages of subjects and repeated for severity and relationship to study drug per treatment group. A subject will be counted only once by the highest severity grade within a system organ class and preferred term, even if the subject experienced more than one AE within a specific system organ class and preferred term. The number of AEs leading to withdrawal and SAEs leading to death will also be summarized.

The incidence of AEs and SAEs will be summarized by body system and treatment group. All AEs and SAEs will be listed by subjects.

Descriptive summary statistics (e.g., n, mean, standard deviation, median, minimum, and maximum for continuous variables; n [%] for categorical variables) for other safety parameters will be summarized by visit. Changes from baseline of safety parameters will also be summarized.

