#### **4.0 RANDOMIZATION AND BLINDING**

This is a multi-center, randomized, double-masked, vehicle-controlled, parallel-group safety and efficacy study. Approximately 128 subjects (64 per treatment arm) will be randomized in the study to complete approximately 96 subjects (48 per treatment arm).

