#### **5.0 SAMPLE SIZE CONSIDERATIONS**

With the assumption that the proportion of subjects that will achieve complete corneal healing for the CSB-001 and vehicle are 60% and 30%, respectively, 48 subjects per arm (a total of 96 subjects) will have 80% power to detect the difference of 30% at a two-sided alpha 0.05 based on a Chi-squared test. With a predicted dropout rate of ~10% and the risk of inadequate numbers of corneal defect images for interpretation by the central reading center at key visits (Day 0, Week 8, and Week 10), approximately 128 subjects will be randomized at 1:1 ratio (CSB-001: vehicle).

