### **7.0 GENERAL STATISTICAL CONSIDERATIONS AND DEFINITIONS**

#### **7.1 General Consideration and Table Layout**

The controlled phase data will be evaluated when all subjects complete the controlled phase. Data from the controlled phase will be cleaned and locked at data point level. The study will be unblinded and the controlled phase analyses will be performed. Efficacy and safety summary tables will be displayed by treatment group of CSB-001 or Vehicle.

Following completion of the last subject in the open-label, uncontrolled phase, efficacy and safety analyses based on the safety analysis set of the uncontrolled phase will be performed for the uncontrolled phase. Efficacy and safety summary tables will be displayed as a single treated group.

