**10.3 Intraocular Pressure (IOP)**

IOP data will be presented in a listing.

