**10.5 Pinhole Distance VA**

Pinhole data will be presented in a listing, besides being summarized as an exploratory endpoint.

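### IOP has no planned summary, TEAEs have no cut at the first open-label dose, and visual acuity is summarized only as a study-eye efficacy measure

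*SAP*

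**What the plan says.** **Adverse events.** SAP 10.1 counts as a TEAE "any AE that occurs on or after the start time of the first study drug administration". It gives no end point and no restart at the open-label phase. SAP 7.4 anchors imputed adverse event start dates to the first dose of study medication, also without regard to phase. Protocol 12.1 collects adverse events from consent to the end of the study, with onset date and time.

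**Phases.** Only vehicle subjects can enter the open-label phase; CSB-001 subjects who are not healed leave the study (SAP 3.0). SAP 6.4 and 6.5 define a safety set for each phase, and SAP 7.2 a baseline for each. SAP 7.1 locks and analyses the controlled phase by arm once all subjects have completed it. It analyses the open-label phase later: "Efficacy and safety summary tables will be displayed as a single treated group".

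**IOP and VA.** Both are named safety parameters (Protocol 11.2.1, SAP 2.2.4) and both belong to the safety part of the primary objective (SAP 2.1.1). Protocol 13.4 asks for by-visit summaries of such parameters and adds: "Changes from baseline of safety parameters will also be summarized". SAP 10.3 says only: "IOP data will be presented in a listing". SAP 10.5 says: "Pinhole data will be presented in a listing, besides being summarized as an exploratory endpoint". SAP 1.0 gives the SAP precedence over the protocol's analysis plan.

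**The concern.** The primary objective is to compare safety as well as efficacy with vehicle. Two things stand in the way of a clean comparison.

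First, because the SAP takes precedence, the IOP summary in Protocol 13.4 drops out. A shift in IOP between arms would have to be found by reading individual lines. VA keeps a summary, but one built to show efficacy.

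Second, the crossover is one-sided. Open-label events can occur only in subjects randomized to vehicle, and these subjects are unmasked before they enter. If the TEAE flag is programmed from SAP 10.1 alone, an event on open-label CSB-001 qualifies under the vehicle assignment. An event from the vehicle period qualifies again in the single-group CSB-001 table. The first would blur the randomized comparison; the second would distort the open-label profile, which SAP 2.1.2 gives as the purpose of that phase.

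**Working it through.** **1. IOP.** Set side by side, Protocol 13.4 requires a by-visit summary and change from baseline, while SAP 10.3 provides a listing. Slit-lamp and fundus findings are summarized by visit and by eye (SAP 10.2, 10.4), so the omission is not a general policy. SAP 11.0 covers later departures from the SAP and does not explain this one. The schedule has IOP in both eyes at Day 0, Week 8 and early exit, so the missing table covers one scheduled post-baseline visit plus early exits.

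**2. VA.** The summary that SAP 10.5 keeps is the one in SAP 2.2.3: change from baseline in the study eye at Weeks 4 and 8, and at Week 10 in a subset. The letter-change categories in SAP 2.2.2 and 2.2.3 are gains. The primary population is the full analysis set, which leaves out subjects who are not stage 2 or 3 by the reading center and those with no post-baseline images (SAP 6.1), even if dosed. The schedule collects study-eye VA at Weeks 1, 2, 3, 4, 6, 8 and 10, and VA in both eyes at Day 0, Week 8 and early exit. No safety-set or non-study-eye summary is planned.

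**3. Where the TEAE rule is silent.**
- *Timing of the lock.* The controlled-phase analysis waits for the last subject, so early crossovers may already have open-label events in the database.
- *Shared visit day.* The Week 8 or Week 10 controlled visit can also be open-label Day 0, with the first open-label dose given in the office (Protocol 6.2.1). One date then belongs to both phases.
- *Missing start dates.* Under SAP 7.4 a wholly missing start date becomes the first study dose unless the event ended on or before it. For a crossover subject that is the first vehicle dose, even if the event arose on CSB-001. A missing day usually becomes the first of the month, which can precede a crossover later in that month.
- *Worsening.* Nothing covers an event that starts on vehicle and worsens on CSB-001.

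**4. Size on a literal reading of SAP 10.1.** The inputs come from the sample-size plan. SAP 5.0 assumes healing "for the CSB-001 and vehicle are 60% and 30%, respectively, 48 subjects per arm (a total of 96 subjects) will have 80% power". That figure reproduces with a continuity-corrected chi-squared test: power at 48 per arm is 79.6% by normal approximation and 80.0% by exact enumeration. SAP 4.0 plans 64 per arm. The point does not depend on the power; it uses only 64 and 30%.

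Assumptions: no dropout; the 30% rate (reading center, sustained healing) also describes the investigator's call, which decides eligibility; non-responders are identified at Week 8; open-label dosing lasts 8 weeks.
- Eligible to cross over: 64 × 0.70 = 44.8.
- Vehicle controlled-phase follow-up: 64 × (0.30 × 10 + 0.70 × 8) = 64 × 8.6 = 550.4 person-weeks.
- CSB-001 time if all cross over: 44.8 × 8 = 358.4 person-weeks.
- Share: 358.4 / (550.4 + 358.4) = 358.4 / 908.8 = 39.4%.
- If half cross over: 179.2 / (550.4 + 179.2) = 179.2 / 729.6 = 24.6%.

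SAP 10.1 counts subjects with at least one event, so person-time is only indirect. As an illustration, assume the same constant hazard in both arms and on both treatments, with 8-week incidence f. A crossover subject followed for 16 weeks has incidence 1 − (1 − f)². At f = 20% this is 36%, and the vehicle arm would read:
- all cross over: 0.30 × 20% + 0.70 × 36% = 31.2%;
- half cross over: 0.65 × 20% + 0.35 × 36% = 25.6%.

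For half to all crossing over, f = 10% gives 13.1% to 16.3%, and f = 40% gives 48.4% to 56.8%. The values of f are assumed; the documents give none.

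**The case against.** The best reply is that the SAP must be read as a whole. SAP 6.4, 6.5, 7.1 and 7.2 separate the phases by population, lock, table layout and baseline. On that reading SAP 10.1 only screens out pre-dose events, and the phase decides the table. This stands as to intent. A reader might infer that the SAP ignores the crossover, or that its safety rules cannot support the comparison with vehicle. The documents do not bear that out: adverse events, slit-lamp, fundus and tolerability are all summarized, and SAP 7.1 displays safety tables by arm. But those sections say who is in each set and when each analysis runs. They do not say which event belongs to which phase, and the imputation rule can place an open-label event in the vehicle period.

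A reader might also infer that VA is reduced to a listing. SAP 10.5 keeps a summary, and study-eye change from baseline would show average loss as well as gain. Nor do the documents require a table of subjects losing a fixed number of letters. What remains is the population, the visits and the non-study eye, which is the lesser matter because only the study eye is treated.

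Counting ten weeks for each crossover would give 448 / 998.4, about 45%. That is not time on drug: dosing lasts eight weeks, and the Week 10 visit is off treatment and only for those healed at Week 8.

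On IOP there is no good reply, except that only one post-baseline visit is scheduled and the values remain listed.

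**Conclusion.** The point holds in three parts of unequal weight.

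IOP holds in full. A named safety parameter in the primary objective loses the summary that the protocol requires, and no reason is given.

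The TEAE part holds as a missing operational rule. The 39% is a ceiling for a literal reading that SAP 7.1 does not intend. It rests on full crossover, no dropout and a 70% non-healing rate as judged by the investigator; a higher non-healing rate would raise it. Vehicle subjects who heal by Week 8 and relapse by Week 10 would add off-drug follow-up and lower it. It shows what the missing rule could allow, and does not predict bias in the planned tables.

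The VA part is the narrowest: the safety summary in Protocol 13.4 is replaced by a study-eye efficacy summary. None of the three parts touches the primary efficacy analysis or the sample size.

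**What to change.** 1. **SAP 10.3:** add an IOP summary by visit, arm and eye, with observed value and change from baseline, in the Safety Analysis Set.
2. **SAP 10.1:** define TEAEs by phase. Controlled phase: onset or worsening from the first controlled dose until the first open-label dose or study exit, whichever comes first. Uncontrolled phase: onset or worsening on or after the first open-label dose. Use the recorded onset time to assign events on a shared visit day.
3. **SAP 7.4:** make start-date imputation phase-specific, for example by anchoring to the first dose of the phase in which the event was first reported, with a stated default where the phase cannot be established.
4. **SAP 10.5:** add the Protocol 13.4 VA summary, by visit and as change from baseline, in the Safety Analysis Set, for both eyes where collected.

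The cost is SAP wording and a few standard tables. IOP, VA and adverse event onset date and time are already collected, so no new data are needed. The change should be made before the controlled-phase data are locked and unblinded.
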